8.9 Columbia Suicide Severity Rating Scale (C-SSRS)

The Columbia Suicide Severity Rating Scale (C-SSRS) is a brief Investigator-administered questionnaire that provides for the identification, quantification and standardized assessment of the occurrences and severity of suicidal ideation and behavior.

The "Baseline/Screening" version of the C-SSRS will be administered to all subjects at the Screening Visit. The "Since Last Visit" version will be used at all subsequent study visits (and Early Termination, if necessary). The Investigator or other designated, qualified individual at the clinical site will perform these assessments).

The frequency of suicidality using the C-SSRS will be summarized for each visit for each of the following outcomes:

- Number of subjects reporting at least one occurrence of suicidal ideation or behavior.
- Number of subjects reporting any type of suicidal behavior.

- Number of subjects reporting any type of suicidal ideation.

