### 3.2.2 Safety Endpoints

All subjects who enter the study will be assessed for safety. Safety will be monitored by adverse events (AEs) assessed at each visit. In addition, the Columbia Suicide Severity Rating Scale (C-SSRS) will be administered at Baseline and all subsequent scheduled visits to assess emergent suicidal thoughts or behaviors. Medical history will capture all medical conditions at Visits 1 (Screening) and 2 (Baseline). Physical examinations and clinical laboratory tests will be conducted at Screening and at Visit 7 (End of Study) and also can be conducted at any subsequent visit as deemed necessary by the Principal Investigator. Safety will be assessed by the following measures throughout the study:

- Vital sign changes
- Changes in weight
- Incidence and severity of AEs
- Incidence of clinically significant changes from Baseline in the C-SSRS
- Electrocardiogram (ECG) changes
- Laboratory values

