### **9.8.4 Other Safety Variables**

Concomitant medications taken during study will be categorized by World Health Organization (WHO) classification for therapeutic class and drug name and summarized by number and percentage of subjects by treatment group. Prior medications will also be summarized.

C-SSRS data will be listed.

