8. SAFETY EVALUATION

All subjects who enter the study will be assessed for safety. Safety will be monitored by AEs assessed at each post-dose visit, physical examination, vital signs, electrocardiogram and clinical laboratory tests. In addition, the Columbia Suicide Severity Rating Scale (C-SSRS) will be administered at Screening, Baseline and all subsequent scheduled visits to assess emergent suicidal thoughts or behaviors.

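### The C-SSRS counts in SAP 8.9 do not deliver the change-from-Baseline measure that the protocol names, and that change is never defined

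*SAP*

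**What the plan says.** Protocol 3.2.2 lists among the safety measures "Incidence of clinically significant changes from Baseline in the C-SSRS", and Protocol 6.4 repeats it. The stated purpose of repeating the scale is to detect emergent events. Protocol 3.2.2 has it given at Baseline and "all subsequent scheduled visits to assess emergent suicidal thoughts or behaviors". SAP 8 says that it "will be administered at Screening, Baseline and all subsequent scheduled visits to assess emergent suicidal thoughts or behaviors".

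The analysis text is much thinner. Protocol 9.8.4 says only "C-SSRS data will be listed", and the Synopsis agrees. SAP 8.9 goes one step further: "The frequency of suicidality using the C-SSRS will be summarized for each visit for each of the following outcomes". The outcomes are a combined count of subjects with ideation or behavior, then "Number of subjects reporting any type of suicidal behavior" and "Number of subjects reporting any type of suicidal ideation". SAP 12.2 records no change from the protocol's analyses.

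Three other provisions matter here:

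- Exclusion 23 (Protocol 4.2) bars an ideation score of 2 or more, and self-injurious behavior in the past year. A score of 1 is not barred.
- The baseline form of the scale is used at Screening. Every later assessment, including Visit 2, uses the form that covers the interval since the previous visit (Protocol 6.4.7, SAP 8.9).
- Protocol 9.8 has all safety data described by treatment group on the Safety Population.

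**The concern.** The protocol names an incidence of change, and the SAP tabulates a prevalence at each visit. The two answer different questions. For a CNS stimulant, the safety question is how many subjects in each arm developed suicidal ideation or behavior, or became worse, after starting treatment. A visit-by-visit count of anyone with any ideation does not answer that. It mixes ideation that was there at entry with ideation that is new, treats a mild and a more severe report alike, and does not show whether positive counts at different visits come from the same subject.

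If nothing is added, the study report will contain no summary of the measure that the protocol names. Anyone wanting it would have to build it from listings after unblinding, with a definition of change chosen at that point. SAP 10 would class such an analysis as exploratory.

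**Working it through.** The plan states no C-SSRS rate or figure to reproduce, so the check compares texts, followed by an illustration on stated assumptions.

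**Step 1. What the measure needs, and what SAP 8.9 supplies**

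| Needed for an incidence of clinically significant change | In SAP 8.9 |
|---|---|
| A defined baseline | Not stated. Screening and Visit 2 both precede dosing and use different forms |
| A definition of clinically significant change | Absent from both documents |
| A within-subject comparison with baseline | Absent |
| Severity of ideation | Pooled into any type |
| Each subject counted once over treatment | Absent; counts are per visit |
| Treatment group and population | Supplied by Protocol 9.8 and SAP 8.2 |

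**Step 2. What the per-visit counts cannot show**

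- *Recurrent versus new ideation.* A subject who enters with score 1 and has it again in each interval is counted at each of Visits 3 to 7, up to five times. At any one visit this subject adds 1, as a new case does.
- *Worsening.* A subject who goes from score 1 to a higher score adds 1, as does a subject who stays at 1.
- *Subjects over the treatment period.* Visit counts of 1, 0, 1, 0, 1 fit one subject with three episodes or three subjects with one each.
- *Behavior.* This is much less affected. The later forms cover only the interval since the last visit, so behavior reported on them is not carried forward. What is missing for behavior is the once-per-subject count.

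**Step 3. Illustration of size**

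Inputs: N = 104 randomized per arm (Protocol 9.1, SAP 2.7); the Safety Population may be slightly smaller. Two inputs are assumptions, because the documents give no rates: e, the share of an arm whose score-1 entry ideation recurs in every interval; and w, the share of the remaining subjects with new ideation at a given visit.

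- Ideation count at a visit = N·e + N·(1 − e)·w
- Share that is new = N·(1 − e)·w ÷ that count

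Example with e = 5% and w = 3%: 104 × 0.05 = 5.2 recurrent; 104 × 0.95 × 0.03 = 2.96 new; count 8.2; share new 2.96 ÷ 8.16 = 36%.

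| e | Count at a visit, w = 1% / 3% / 5% | Share new, w = 1% / 3% / 5% | Recurrent subject-visits over Visits 3 to 7 (5·N·e) |
|---|---|---|---|
| 0% | 1.0 / 3.1 / 5.2 | 100% / 100% / 100% | 0 |
| 2% | 3.1 / 5.1 / 7.2 | 33% / 60% / 71% | 10.4 |
| 5% | 6.2 / 8.2 / 10.1 | 16% / 36% / 49% | 26.0 |
| 10% | 11.3 / 13.2 / 15.1 | 8% / 21% / 31% | 52.0 |

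With no recurring entry ideation, the visit count is the new-ideation count for that visit. Once a few percent of subjects have it, the count reflects entry status as much as emergence, and the table does not show which case applies.

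**The case against.** The strongest reply is that new cases can be found elsewhere. SAP 3 lists all data by subject, treatment group and time point. The adverse event definition in Protocol 7.1 includes a prior condition that becomes more severe or frequent, and SAP 8.4 tabulates such events by arm with each subject counted once per preferred term. This stands in part. But a listing is not an incidence by arm, and no rule turns a positive C-SSRS into an adverse event. SAP 8.6 does make that link for abnormal physical examination findings.

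It can also be said that SAP 8.9 already exceeds the protocol's own analysis text, which only lists the data, and that nothing here is tested. Both are true. They limit the weight of the point, but the named measure still has no summary.

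A reader might infer more than the documents support:

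- *That the table omits treatment group.* SAP 8.9 does not mention it, but Protocol 9.8 supplies it.
- *That every subject entering with score 1 is counted at all later visits.* Each later form covers one interval, so the subject counts only where ideation recurs.
- *That the table would rank the arms wrongly.* Suppose one placebo subject has recurring score-1 ideation (1, 1, 1, 1, 1) and three AR19 subjects have one new episode each (1, 0, 1, 0, 1). Emergent incidence is 0/104 against 3/104, while positive subject-visits are 5 against 3. That reversal needs the rows to be added, which the SAP does not plan. Row by row the arms tie at Visits 3, 5 and 7 and differ by one subject at Visits 4 and 6. Entry ideation is also balanced in expectation by randomization.
- *That the Screening count has a different look-back period.* The documents show a different form there, but do not state its recall period.

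**Conclusion.** The point holds in a limited form. No planned summary gives the C-SSRS measure named in Protocol 3.2.2 and 6.4, and the change it refers to is undefined. The per-visit counts in SAP 8.9 cannot replace it for ideation: recurring score-1 ideation and new ideation look alike, and worsening from score 1 is hidden. Listings and adverse event tables cover this only partly.

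The practical size depends on how many subjects enter with score 1 and report it again, which the documents do not tell us. On the assumed ranges, new cases make up 8% to 71% of the visit count when recurring entry ideation is present, and all of it when there is none. Efficacy conclusions, alpha and sample size are untouched. This should be corrected before the SAP is signed, but it does not threaten the trial's main result.

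**What to change.** Amend SAP 8.9 as follows:

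1. Define the C-SSRS baseline, for example the highest ideation category before first dose at Screening or Visit 2.
2. State what the sponsor counts as a clinically significant change, so that the protocol's term has a fixed meaning before unblinding.
3. On the Safety Population, by treatment group, tabulate the number and percentage of subjects, each counted once over all assessments after first dose (Visits 3 to 7, Early Termination and any unscheduled assessment), with (a) new or worsened ideation relative to that baseline and (b) any suicidal behavior. If the definition in item 2 differs from (a), add a row for it.
4. Keep the three per-visit counts as supportive.
5. Note in SAP 12.2 that C-SSRS summaries are added to the listing planned in the protocol.

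The cost is SAP wording and one small descriptive table. The data are already collected, and no visit, assessment or test is added. The change is consistent with SAP 8.7, which already sets explicit change criteria for vital signs.

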9. PHARMACOKINETIC EVALUATION

Exposure-response relationships using population pharmacokinetics will be explored. To aid the population pharmacokinetic analysis, two blood plasma samples will be collected from all subjects. The samples collected will include pre-dose up to approximately 6 hours following drug administration on planned subject visit days (Visit 6 and Visit 7). Covariates such as age, weight, liver function (AST and ALT), CYP 2D6 metabolizer status, and race and their effect on AR19 pharmacokinetic parameters will be explored. The pharmacokinetic analysis and reporting will be covered in a separate SAP and report.

10. OTHER ANALYSES

No other analyses are planned for this study. However, any additional analyses performed after finalization of the SAP will be considered exploratory and will be identified as such in the clinical study report (CSR).

11. INTERIM ANALYSES AND DATA MONITORING

No interim analyses or official data monitoring are planned for this study.

12. CHANGES TO STUDY CONDUCT OR ANALYSES PLANNED IN THE PROTOCOL

12.1 Changes in the Conduct of the Study

This SAP is based on Version 3.0 of the AR19.004 clinical study protocol dated August 20, 2018. No changes in the conduct of the study are planned from this version of the protocol.

12.2 Changes in the Analysis Planned in the Protocol

This SAP is based on Version 3.0 of the AR19.004 clinical study protocol dated August 20, 2018. No changes in the analyses of the study are planned from this version of the protocol.

13. REFERENCES

1. US Federal Register. (1998) International Conference on Harmonization; Guidance for Industry: Statistical Principles for Clinical Trials. Department of Health and Human Services: Food and Drug Administration. Federal Register, Vol. 63, No. 179, September 16, 1998, page 49583.
2. US Federal Register. (1996) International Conference on Harmonization; Guidance for Industry: Structure and Content of Clinical Study Reports. Department of Health and Human Services: Food and Drug Administration. Federal Register Vol. 61, July 17, 1996, page 37320.

14. APPENDICES**14.1 Schedule of Events**

Visit Name ^a	Screen	BL	Week 1	Week 2	Week 3	Week 4	End of Study Week 5	Follow-up Phone Call Week 6	Early Termination
Visit Number	1	2	3	4	5	6	7	8	
Study Day Assessment	-30 to -1	1	8 ±2d	15 ±2d	22 ±2d	29 ±2d	36 ±2d	7 days post V7 +2d	
Subject consent	X								
Eligibility assessment	X	X							
Previous medications	X								
Medical history	X	X							
Demographics	X								
MINI	X								
CAADID	X								
DSM-5™ diagnosis	X								
AISRS	X	X	X	X	X	X	X		X
CGI-S	X	X	X	X	X	X	X		X
CGI-I			X	X	X	X	X		X
Height	X								
Body weight	X	X					X		X
BMI	X								
Vital signs ^b	X	X	X	X	X	X	X		X
12-lead ECG	X						X		X
Physical examination	X						X		X
Hematology	X						X		X
Serum chemistry	X						X		X
Blood alcohol	X								
HbA1c	X								
HCV RNA ^c	X								
Pregnancy ^d	X	X		X		X	X		X
Urinalysis ^d	X						X		X
CYP 2D6 testing ^d		X							
Drugs of abuse test	X	X							
C-SSRS (BL/Screen)	X								
C-SSRS (FU)		X	X	X	X	X	X		X
BRIEF-A		X					X		X
DERS		X					X		X
ASQ		X					X		X
PK Sampling						X	X		
Dispense study drug/training		X	X	X	X	X			
Drug accountability			X	X	X	X	X		X
Adverse events			X	X	X	X	X	X	X

Visit Name ^a	Screen	BL	Week 1	Week 2	Week 3	Week 4	End of Study Week 5	Follow-up Phone Call Week 6	Early Termination
Visit Number	1	2	3	4	5	6	7	8	
Study Day Assessment	-30 to -1	1	8 ±2d	15 ±2d	22 ±2d	29 ±2d	36 ±2d	7 days post V7 +2d	
Concomitant medication	X	X	X	X	X	X	X	X	X

^a The interval between each visit for Visits 3-6 must not exceed 9 days.

^b At all visits, vital signs include blood pressure and pulse assessments (in triplicate via automated machine). At Screening, vital signs also include respiratory rate and temperature.

^c Females of childbearing potential only. Serum pregnancy test will be performed at Visit 1. Urine dipstick pregnancy test is performed onsite at Visits 2, 4, 6, and 7 or early termination and may be performed at any time during study participation, if pregnancy is suspected.

^d CYP 2D6 genetic testing for randomized subjects who opt in only. Subjects choosing to opt out are still eligible for the study.

^e Hepatitis C virus RNA for subjects who report a positive history of hepatitis C that is now completely treated.

^f Specific gravity, pH, urobilinogen, leucocyte esterase, nitrite, bilirubin, ketones, hemoglobin, glucose, and total protein; if the dipstick is positive for protein, nitrite, leucocytes and/or blood, the sample will be sent for microscopic analysis including: WBC, RBC, epithelial cells, bacteria, yeast, crystals, hyaline casts, granular casts, mucous threads, and waxy casts.

AISRS = Adult ADHD Investigator Rating Scale; ASQ = Affective Style Questionnaire; BL = baseline; BMI = body mass index; BRIEF-A = Behavior Rating Inventory of Executive Function – Adult Version; CAADDID = Conners Adult ADHD Diagnostic Interview for DSM-IV; CGI-I = Clinical Global Impression of Improvement; CGI-S = Clinical Global Impression of Severity; C-SSRS = Columbia Suicide Severity Rating Scale; CYP = cytochrome P450; DERS = Difficulties in Emotion Regulation Scale; DSM-5™ = Diagnostic and Statistical Manual of Mental Disorders, Fifth Edition; ECG = electrocardiogram; FU = follow-up; HbA1c = glycosylated hemoglobin; MINI = Mini International Neuropsychiatric Interview for Adults; PK = pharmacokinetic

14.2 Adult ADHD Investigator Symptom Rating Scale (AISRS) and Subscales

Subscale	Item
Hyperactivity/Impulsivity	2. Fidget or squirm with hands or feet 4. Leave seat in meetings or other 6. Feel restless or fidgety 8. Difficulty relaxing/unwinding 10. Feel overly active compelled to do things 12. Find yourself talking too much 14. In conversation finish other's sentences 16. Difficulty waiting your turn 18. Interrupt others when they are busy
Inattentiveness	1. Careless mistakes working on boring projects 3. Difficulty keeping attention 5. Difficulty concentrating when spoken to 7. Trouble wrapping up final details of project 9. Difficulty getting things in order 11. Avoid task that requires lots of thought 13. Misplace or have difficulty finding things

	15. Find yourself being distracted by activity
	17. Problems remembering appointments
